IL 8 plays an important role in acute inflammation because it acts as a potential chemotactic agent and neutrophil activator by activating CXCR1 and CXCR2 (Emadi et al., 2005). The reduced IL 8 response induced by LPS in neutrophils has been confirmed in human whole blood translational and non-animal models. This was achieved by exposing neutrophils in vitro to a pro-inflammatory microenvironment containing N-formyl Met Leu Phe, LPS, or IL 8, resulting in a response accompanied by an increase in cell size and pH that leads to a decrease. The detailed kinetics of this degradation can be shown almost in real time by measuring flow cytometry. Overall, we provide a new mechanistic overview of the interaction between IL 8 and neutrophils and explain how IL 8 changes during systemic inflammation.

Meanwhile, MKK6 phosphorylates another MAPK, p38, which leads to the phosphorylation of MK 2 and stabilizes IL 8 mRNA. The activation of the C/EBP signaling pathway is largely still unknown (Matsushima et al., 2022).

CHAPTER III

RESEARCH METHOD

A. Type of Research The type of research used is Clinical Experimental, designed with a Randomized Controlled Trial double blind, with pre and post test design on samples of patients with persistent allergic rhinitis.

B. Place and Time of Research The research is conducted at the Outpatient Clinic of Ear, Nose, Throat Health Science Surgery at the Sebelas Maret University Hospital and the biomedical laboratory of the Faculty of Medicine UNS for the examination of MDA, NF kB, TNF α , Interleukin 6, Interleukin 8. The research will be carried out after obtaining research approval from the dissertation proposal examination board and the Research Ethics Commission.

C. Subjects/Sample of Research Outpatient patients who have undergone anamnesis and physical examination of ENT.

1. Restriction Criteria **Inclusion Criteria:**

- 1) Patients aged 18 – 60 years who have signed informed consent
- 2) Diagnosed with persistent allergic rhinitis with Skin Prick Test or Positive IgE Examination.

Exclusion Criteria:

- 1) The presence of complications in the nose such as nasal septum deviation, polyps, rhinosinusitis
- 2) Have undergone specific immunotherapy for 2 years
- 3) Use of medications that affect allergy test results: antihistamines, corticosteroids, antihypertensive medications, and decongestants
- 4) Pregnancy and Breastfeeding.

Sample Size

The sample size uses the Frederer formula.

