$$\text{Frederer Formula} = (n - 1) (t - 1) \geq 15$$

Explanation: n: sample size of each group: number of groups

According to the Frederer formula, the number of samples required:

$$(n - 1) (t - 1) \geq 15(n - 1) (3 - 1) \geq 15(n - 1) 2 \geq 152n = 17, n = 8.5$$

The number of samples used must be greater than or equal to 9 samples per group. In this study, 10 test samples will be used in each group. This is done to facilitate the author in data analysis calculations, so the total number of samples used in this study is 40 samples.

Sampling Technique

Randomized Control Trial pre and post-test design. Eligible participants/patients who meet the inclusion and exclusion criteria will be randomized. Participants will be grouped into four groups, namely the control group and the treatment group, and then the outcomes will be observed.

F. Implementation/Research Procedure

1. Recruitment of research subjects and randomizationAll patients with persistent allergic rhinitis, Randomization with closed envelopes, Therapy according to the persistent allergic rhinitis algorithm
2. Source of apple fruit extractApple fruit extract is made in the Pharmacy Laboratory of Muhammadiyah University of Surakarta.

3. Preparation of apple fruit extract Polyphenol extract is derived from the fruit of *Mallus sylvestris* mill obtained from apple farmers in Malang. Dried apples are extracted, and re-extracted twice with 50% ethanol. The obtained material is concentrated using a rotary evaporator (Rotavapor, Buchi Labortechnik AG, Switzerland) in a water bath at 40 °C. Furthermore, the extract is adsorbed using Amberlite XAD 16 resin (Brentag, Essen, Germany), and after the evaporation of ethanol, the collected fraction is dried in a vacuum oven SPT 200 (Zeamil, Krakow, Poland) (Mihailović et al., 2018).
4. Measurement of Malondialdehyde (MDA)Measurement of MDA using the Enzyme Linked techniqueItchy noseClinical symptoms in allergic rhinitis.TNSS Checked on the First day and the 14th dayOrdinalRhinorrheaClinical symptoms in allergic rhinitis.TNSS Checked on the First day and the 14th dayOrdinal.

G. Statistical Analysis

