Statistical analysis was conducted using IBM SPSS Statistics for Windows, version 25.0 (IBM Corp., Armonk, NY, USA). Data normality was evaluated using the Shapiro–Wilk test. For normally distributed and homogeneous data, one-way analysis of variance (ANOVA) was applied. When the data were not normally distributed but homogeneous, the Kruskal–Wallis test was used. Comparisons across three time points were performed using repeated-measures ANOVA, with the Friedman test employed as the nonparametric alternative.

REFERENCE

ARIA (Allergic Rhinitis and its Impact on Asthma). 2019. ARIA guideline 2019: treatment of allergic rhinitis in the German health system. Allergol Select. 2019 Dec 30;3(1):22-50. doi: 10.5414/ALX02120E. PMID: 32176226; PMCID: PMC7066682.

Bjermer, Leif; Westman, Marit; Holmström, Mats; Wickman, Magnus C. (2019). The complex pathophysiology of allergic rhinitis: scientific rationale for the development of an alternative treatment option. *Allergy, Asthma & Clinical Immunology*, 15(1), 24 – . doi:10.1186/s13223-018-0314-1

Dalimartha, S. & Adrian, F. (2013). Fakta Ilmiah Buah & Sayur. Jakarta: Penebar Swadya.

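### Section G names only omnibus group tests and time tests with no stated group term: no error-controlled comparison of a treatment group with control, no estimate or interval, and no use of baseline in the group comparison

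*Combined protocol and SAP*

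**What the plan says.** Chapter III, section A describes a double-blind randomized controlled trial "with pre and post test design on samples of patients with persistent allergic rhinitis". The sampling paragraph states: "Participants will be grouped into four groups, namely the control group and the treatment group". The sample-size paragraph adds that "10 test samples will be used in each group", 40 in total, although its formula uses three groups.

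Section G is one short paragraph. After a Shapiro-Wilk check it says: "For normally distributed and homogeneous data, one-way analysis of variance (ANOVA) was applied". The Kruskal-Wallis test is reserved for the case "When the data were not normally distributed but homogeneous". For time it says: "Comparisons across three time points were performed using repeated-measures ANOVA, with the Friedman test employed as the nonparametric alternative".

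The paragraph names no contrast with control, follow-up test, multiplicity method, effect estimate, confidence interval, significance level, or group or group-by-time term. It does not say whether groups are compared on final values, changes or baseline-adjusted values. No other section supplies these. The paragraph runs unbroken from its heading to the reference list, so lost text does not explain the omissions.

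Two further places matter. Section F lists "Therapy according to the persistent allergic rhinitis algorithm" in the step that covers recruitment and randomization. The visible symptom rows of the outcome table read "TNSS Checked on the First day and the 14th dayOrdinal".

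**The concern.** The design exists to show whether a treatment group does better than control. With more than two groups, one-way ANOVA and Kruskal-Wallis test only whether all groups are alike. If they reject, at least one treatment group differs from control, but the test does not identify it or say whether it did better or worse, and it gives no size with uncertainty.

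The time tests do not fill the gap. Friedman has no group factor. Repeated-measures ANOVA can have one, but none is stated. A change over time is not evidence of a treatment effect either: the procedure lists algorithm-based therapy for the disease, so control patients may improve too.

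The baseline measurement, which the pre/post design already pays for, has no stated role in comparing groups. In a trial with 10 patients per group, that can waste a useful amount of precision.

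**Working it through.** **The plan's own figure.** The formula is (n − 1)(t − 1) ≥ 15. With t = 3, n ≥ 15/2 + 1 = 8.5, so 9 per group, as stated. With t = 4, n ≥ 15/3 + 1 = 6. Ten per group gives 40 only with four groups; three would give 30. The group count therefore needs reconciling, but either count makes the between-group tests omnibus.

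**Inputs.** From the documents: 10 per group and four groups. Assumed, because the documents give none: one control and three treatment groups, two-sided 0.05, normal data, effects in SD units, and 80% power for detectable differences.

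**What the omnibus test distinguishes.** The noncentrality is λ = 10 × Σ(μᵢ − μ̄)².
- One treatment group 1 SD better, means (0, 1, 0, 0): μ̄ = 0.25 and λ = 10 × (0.5625 + 3 × 0.0625) = 7.5.
- All three better, means (0, 1, 1, 1): μ̄ = 0.75 and λ = 10 × (0.5625 + 3 × 0.0625) = 7.5.
- Reversing the signs (one or all three worse) leaves λ at 7.5.

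With 3 and 36 df, power is 57.1% in all four cases. The F test alone cannot separate them.

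**Comparisons with control.** The residual df are 4 × 9 = 36. The critical value is 2.028 unadjusted and about 2.452 for Dunnett with three comparisons. The interval half-width is the critical value × √(2/10):
- unadjusted: 2.028 × 0.447 = 0.91 SD
- Dunnett: 2.452 × 0.447 = 1.10 SD

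The detectable difference d solves P(T > critical value) = 0.80, with T noncentral t on 36 df and noncentrality d√(10/2). This gives 1.29 SD unadjusted and 1.48 SD with Dunnett. With three groups (27 df, critical values 2.052 and 2.333) it gives 1.30 and 1.43 SD.

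**What baseline adjustment is worth.** Adjusting for baseline multiplies the residual variance by about 1 − r², at the cost of one df.

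| Assumed pre-post correlation r | Omnibus power, one group 1 SD away (57% unadjusted for baseline) | Detectable difference, ANCOVA with Dunnett |
|---|---|---|
| 0.3 | about 60% | 1.43 SD |
| 0.5 | about 70% | 1.30 SD |
| 0.7 | about 87% | 1.07 SD |

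The power column is simulated. Simulated power at each detectable difference was 80%.

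**Illustrations of what the plan leaves open.** These do not describe stated procedures.
- Separate tests in each group: if all four groups improve equally (0.5 to 1 SD by a third visit, between-visit correlation 0.3 to 0.7), a repeated-measures ANOVA run within each group is significant in some treatment group but not in control in 7–47% of simulated trials. The group-by-time test rejects in about 5%.
- Unadjusted follow-up after a significant ANOVA: with one group truly 1 to 3 SD from control, another group is falsely declared different in 8–9% of trials, against about 3.6% with Dunnett.

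**The case against.** The best counter-argument is that the F statistic would never be read alone. Group means would be reported and would show direction. In simulation with one treatment group 1 SD above control, that group's mean exceeded control in over 99% of significant ANOVAs and was the highest of the four in 99%. This stands. A reader might infer that a significant result would leave direction and size wholly unknown, and the documents do not support that. What is missing is formal attribution to a group with error control, and a planned estimate with an interval. Section G names no summary measure at all.

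A reader might also infer that efficacy will be judged from separate within-group time tests, or from unadjusted pairwise tests after ANOVA. Section G states neither, and its repeated-measures ANOVA could contain a group term. The percentages for those procedures therefore show only why the gap should be closed.

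It is also fair to say that Dunnett and ANCOVA are one acceptable choice among several, and that one control with three treatments is an assumption: the sampling paragraph does not name the arms. Neither point supplies the missing comparison.

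Finally, a reader might conclude that no primary outcome exists, or that the third time point is an error. Introductory text is not available and the outcome table is broken, so both are separate queries.

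**Conclusion.** The point holds in this form. Followed as written, section G would not formally answer the randomized question. It names no error-controlled comparison of any treatment group with control and no estimate or interval, and it gives baseline no role between groups. This rests on the text alone and does not depend on whether there are three or four groups.

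The sizes rest on the assumptions listed in the working. Under them, the omnibus power of 57.1% is the same for benefit and harm, and baseline adjustment would raise it to between about 60% and 87%, depending on the pre-post correlation. The plan should be changed on this point. The omission is remediable at analysis and does not by itself invalidate the data.

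**What to change.** 1. Reconcile the number of groups and identify the control and treatment arms.
2. Base treatment conclusions on each treatment group versus control. The omnibus tests may stay as supporting results.
3. For approximately normal outcomes, such as biomarkers (transformed if needed), use ANCOVA of the final value adjusted for baseline, with Dunnett-adjusted 95% confidence intervals.
4. For ordinal symptom items, compare final scores with a baseline-adjusted proportional-odds model or a tie-corrected rank test, with Holm adjustment. State the effect measure with its 95% interval: a common odds ratio or the probability of a better score. Do not subtract ordinal categories.
5. Where an outcome has three time points, put group and group-by-time in the repeated-measures model, and do not use within-group time tests as evidence of efficacy.
6. Section G is in the past tense. If data are already unblinded, report these comparisons as post hoc.

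**Cost.** More analysis work, and no new patients or visits. The detectable difference rises by about 0.19 SD (1.29 to 1.48 SD) with Dunnett. Baseline adjustment offsets part of this at a correlation of 0.3, nearly all at 0.5 and more than all at 0.7. If only one group differs, by 1.48 SD, Dunnett finds some difference in 81% of trials against 91% for ANOVA; if all three differ by that much, 94% against 91%. The cost for ordinal items depends on ties and is not quantified here.

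### Section G states no between-group test for data with unequal variances and no use of baseline in any group comparison; one pre-specified baseline-adjusted model per biomarker would settle both

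*Combined protocol and SAP*

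**What the plan says.** Section G (Statistical Analysis) in Chapter III is the whole analysis plan. Its rules are:

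- Normality: "Data normality was evaluated using the Shapiro–Wilk test". No level is given, and no test of homogeneity is named.
- Group comparison, first branch: "For normally distributed and homogeneous data, one-way analysis of variance (ANOVA) was applied".
- Group comparison, second branch: Kruskal-Wallis, "When the data were not normally distributed but homogeneous".
- Time: "Comparisons across three time points were performed using repeated-measures ANOVA, with the Friedman test employed as the nonparametric alternative". No group factor and no group-by-time term are stated.

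The design (section A) is a double-blind randomised trial "with pre and post test design on samples of patients with persistent allergic rhinitis", so a baseline value is collected. Section B lists five laboratory markers, "for the examination of MDA, NF kB, TNF α , Interleukin 6, Interleukin 8". On size, the plan says "In this study, 10 test samples will be used in each group". The sampling text says "Participants will be grouped into four groups, namely the control group and the treatment group", and the total is 40. In section F, the symptom (TNSS) items that can be read are ordinal and are checked on the first and the fourteenth day.

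**The concern.** The comparison that randomisation supports is the one between groups. Section G picks its test from the trial data, and for part of the possible data it picks none. If a marker's variances differ, the analyst must choose a test after seeing the results. The variance check that leads there has neither a name nor a level.

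Section G also does not define the quantity that ANOVA or Kruskal-Wallis compares. It could be the post-treatment value or the change from baseline. With 10 patients per group, that choice and any baseline adjustment can move power by much more than the choice between ANOVA and Kruskal-Wallis does. What is at stake is an undetermined group comparison and, under some correlations, avoidable loss of power.

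**Working it through.** **1. The plan's own figures.** Section G contains no number to reproduce. The size does reproduce: (n − 1)(3 − 1) ≥ 15 gives n ≥ 8.5, so at least 9 per group. The plan uses 10, and 10 × 4 = 40. (The formula uses three groups where the sampling text has four, which is a separate matter.) No SD, correlation, effect, alpha or power is stated, so every input below is an assumption.

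**2. Coverage of the test rule.**

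| | Homogeneous | Not homogeneous |
|---|---|---|
| Normal | one-way ANOVA | none stated |
| Not normal | Kruskal-Wallis | none stated |

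If the word for homogeneity in the Kruskal-Wallis sentence is a slip, the lower right cell is filled. The upper right cell stays empty, and the homogeneity test is still unnamed. The repeated-measures sentence does not fill either cell: it is worded as a comparison of time points, and the Friedman test cannot compare independent groups.

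**3. How often the empty cells are reached.** Assumed: 4 × 10, log-normal markers, Levene test at 0.05, log-SD 0.3 to 1.0, raw post-treatment values.

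| Setting | Median-centred Levene | Mean-centred Levene |
|---|---|---|
| No effect | about 4% | 10–34% |
| Graded effect (medians 1/0.8/0.65/0.5) | 8–18% | 34–45% |
| Log values | 3% | 7% |

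The mean-centred excess with no effect is mostly the test reacting to skewness. With normal data and one SD at 2 to 3 times the others, Levene rejects in 38–78% (median-centred) or 52–87% (mean-centred) of trials.

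**4. What the gap costs in type I error.** Take log-normal data with equal log-SDs and no effect, and let the analyst pick the most favourable of four tests whenever Levene fails. Overall type I error is then .054–.062 (median-centred) or .057–.081 (mean-centred). With normal data and SD ratios 1:1:1:2 and 1:1:1:3, ordinary ANOVA run regardless gives 6.8% and 8.9%, Kruskal-Wallis 5.2% and 6.0%, and Welch ANOVA 5.1% and 5.1%.

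**5. What the choice of outcome costs in power.** Assumed: 4 × 10, log scale, equal SD σ before and after, correlation ρ, medians 1/0.8/0.65/0.5, alpha 0.05. The log means are 0, −0.223, −0.431 and −0.693, with mean −0.337. The sum of squared deviations is .1134 + .0129 + .0088 + .1270 = .262. The noncentrality is λ = 10 × .262 / (σ²·v), where v = 1 for post values, 2(1 − ρ) for change and 1 − ρ² for baseline adjustment.

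At ρ = 0.6, v is 1, 0.8 and 0.64. At σ = 0.5, λ is 10.5, 13.1 and 16.4.

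| Analysis (ρ = 0.6) | Noncentral F, σ = 0.5/0.7/1.0 | Simulation |
|---|---|---|
| Post-only log ANOVA | .732/.425/.221 | about .72/.42/.22 |
| Change score | .832/.518/.270 | .83/.52/.28 |
| Baseline-adjusted, ordinary errors | .910/.621/.331 | .90/.61/.33 |
| Baseline-adjusted, HC3 | – | .88/.57/.31 |

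The formula for the adjusted model ignores chance baseline imbalance, so it runs slightly high. The plan's rule on raw post values (ANOVA or Kruskal-Wallis chosen by Shapiro-Wilk, run whatever the variances) gives .70/.38/.20. Moving to log ANOVA without a gate therefore adds only about .02 to .04. The rest of the gain comes from baseline.

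At ρ = 0.3 and σ = 0.5, v is 1, 1.4 and 0.91. Noncentral F gives .732 (post), .570 (change) and .775 (adjusted). Simulation gives about .73, .56 to .58 and .76, and .73 with HC3.

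**The case against.** The best defence is that much of this rests on silence. Section G never says what ANOVA is run on. In a pre/post design change scores are a natural reading, and a repeated-measures ANOVA with groups as a between-patient factor may be what was meant. The variable definitions that might settle this stand just before section G, where the text is broken by extraction. This stands. A reader might infer that the trial ignores baseline, but the documents support only that its use in a group comparison is not stated.

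A reader might also infer that the homogeneity gap seriously inflates false positives. Step 4 does not show that: with equal log-SDs the excess is small to moderate even when the most favourable test is picked.

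It is tempting, too, to cite the error rates of a baseline-adjusted model with ordinary standard errors when variances differ. Those rates describe a model that the plan does not contain. They bear on how to build the replacement and show no defect in the sponsor's text.

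Finally, the power gain depends on how the plan is read and on a correlation that the documents do not give. Against change scores at ρ = 0.6, the HC3 model gains about .03 to .05 (.88 − .83, .57 − .52, .31 − .28). Against post-only ANOVA at ρ = 0.3, it gains almost nothing.

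The ambiguity itself remains: none of these readings is fixed in advance.

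**Conclusion.** The point holds in a limited form. As written, section G has no between-group test for unequal variances, names no homogeneity test, gives the time-point sentence no group factor, and states no use of baseline between groups. The gap in the test rule is mainly a drafting fault with a small type I error cost.

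The more useful part is the undefined outcome. At assumed ρ = 0.6, the HC3 baseline-adjusted model has .09 to .16 more power than post-only log ANOVA (.31 − .22 to .88 − .72). At ρ = 0.3 it matches post-only ANOVA and beats change scores, about .73 against .57 at log-SD 0.5. With HC3 it is about level with or better than both simpler readings at these two correlations, so pre-specifying it is the safer choice.

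The sizes rest wholly on assumed log-normal markers, a graded effect and the stated SDs and correlations. This should be changed, with medium confidence.

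**What to change.** For each of the five biomarkers, replace the pretest-driven choice with one pre-specified comparison of the four groups: a linear model of the log post-treatment value on group and log baseline, with HC3 standard errors.

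- Name one post-treatment time for this analysis. First reconcile the three time points of section G with the day 1 and day 14 of section F.
- Report the overall group test first, then geometric mean ratios versus control with 95% confidence intervals. Three ratios for each of five markers make 15 intervals, so state the multiplicity control, for example Holm across the three arms within a marker, and say how the five markers are ranked or adjusted.
- Keep Shapiro-Wilk and residual plots as diagnostics that do not change the test.
- State a separate rank-based or ordinal method for the TNSS items, which a log model does not suit.

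Minimal fallback: Welch ANOVA on log values without a variance gate, with the compared quantity (post value or change) named. With log-SD ratios of 2 to 3 its type I error is .047–.053, against .064–.074 when it is used only after a failed Levene test. It leaves baseline unadjusted. On post values with equal variances its power is .69/.39/.21, against .73/.42/.22 for log ANOVA.

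Cost: a few sentences and no new data. Effects become ratios. HC3 loses about 1 to 4 points of power when variances are equal. If a marker is in fact normal with additive effects (assumed means 100/90/80/70, SD 25, ρ = 0.6), the log model has power .70, against .76 for the same model on raw values and .60 for raw ANOVA without baseline.

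### Section G states no baseline-adjusted comparison of a treatment arm with control, and its Friedman test cannot show an effect of the extract

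*Combined protocol and SAP*

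**What the plan says.** Chapter III, G (Statistical Analysis) is a single paragraph. After a normality check it gives two pairs of tests.

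- Group tests: for normal, homogeneous data "one-way analysis of variance (ANOVA) was applied". Kruskal-Wallis is the alternative, "When the data were not normally distributed but homogeneous".
- Time tests: "Comparisons across three time points were performed using repeated-measures ANOVA, with the Friedman test employed as the nonparametric alternative".

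The paragraph names no outcome, day, covariate, group-by-time term, or contrast of a treatment arm with control.

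The design sections set the context. Under Sampling Technique the trial is a "Randomized Control Trial pre and post-test design", and "Participants will be grouped into four groups, namely the control group and the treatment group, and then the outcomes will be observed". Under Sample Size, "In this study, 10 test samples will be used in each group". The legible symptom items (itchy nose, rhinorrhea) are ordinal TNSS items scored on day 1 and day 14. Section B lists five laboratory markers (MDA, NF-kB, TNF-alpha, IL-6, IL-8), whose sampling days are not legible in the available text.

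**The concern.** The trial asks whether an extract arm does better than control. Neither pair of tests, as written, answers that.

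- An overall four-group p-value does not show which arm differs from control.
- The group tests are stated without use of the day-1 value, which the design already collects.
- The time tests are stated without a group-by-time term. Repeated-measures ANOVA could carry one. Friedman cannot, so it is not a nonparametric substitute for a comparison of arms over time.

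Section F.1 refers to therapy by the persistent-rhinitis algorithm. If that is given in every arm, scores can fall in all of them, and a significant time test could be read as an extract effect. Leaving the contrast and the handling of baseline open also lets them be chosen after the data are seen.

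**Working it through.** **Inputs from the documents.** Four groups of 10, so 4 × 10 = 40, which matches the stated total. The plan's minimum per group reproduces: (n − 1)(3 − 1) ≥ 15 gives n ≥ 8.5, rounded up to 9. That rule uses no effect size, SD or power, so the plan has no power figure to reproduce.

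**Assumptions.** Test level 0.05; one control and three treatment arms; within-patient correlation ρ of 0.3, 0.5 or 0.7. For the power figures, one arm is better by 1.0 SD. The ordinal item is scored 0–3, from a latent normal cut at −1.2, −0.2 and 0.8, with a shared fall of 0.5 SD.

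**Step 1: what Friedman detects.** Simulation with three occasions and ρ = 0.5:

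| Setting | Friedman, arms pooled | Friedman, one arm of 10 | Kruskal-Wallis, last value | ANOVA, last value | ANCOVA |
|---|---|---|---|---|---|
| All arms fall 1 SD, no arm effect | 99.8% | 59% | about 5% | about 5% | about 5% |
| Arms shift by −0.75, −0.25, +0.25, +0.75 SD, mean change zero | 4% | 7.5% | 78% | 82% | 92% |

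Pooled Friedman nearly always rejects when no arm effect exists, and stays near 5% when the arms differ but the average change is zero.

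**Step 2: overall group test, normal outcome.** With one arm shifted by 1 SD, the deviations from the mean are 0.75 once and 0.25 three times.

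- ANOVA on day 14: noncentrality λ = 10 × (0.75² + 3 × 0.25²) = 10 × 0.75 = 7.5, on 3 and 36 df.
- ANOVA on change: λ = 7.5 / [2(1 − ρ)] = 5.36 / 7.5 / 12.5, on 3 and 36 df.
- ANCOVA: λ = 7.5 / (1 − ρ²) = 7.5/0.91, 7.5/0.75, 7.5/0.51 = 8.24 / 10.0 / 14.7, on 3 and 35 df.

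The noncentral F distribution gives 57%, then 43 / 57 / 81%, then 61 / 71 / 87%. The ANCOVA values are slight upper bounds because they ignore chance baseline imbalance. Simulation, good to about one or two points, gives:

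| Overall test, 1.0 SD | ρ = 0.3 | ρ = 0.5 | ρ = 0.7 |
|---|---|---|---|
| ANOVA, day 14 | 57% | 57% | 57% |
| ANOVA, change | 41% | 58% | 82% |
| ANCOVA | 60% | 69% | 87% |
| Kruskal-Wallis, day 14 (0–3 item) | 44% | 44% | 44% |
| Kruskal-Wallis, change (0–3 item) | 26% | 33% | 45% |
| Rank ANCOVA, Quade (0–3 item) | 48% | 55% | 66% |

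Type I error of these tests is near 5%. At 0.5 SD all powers are low: ANOVA on day 14 17% against ANCOVA 18 / 20 / 29%, and Kruskal-Wallis on day 14 13–14% against rank ANCOVA 15 / 17 / 21%.

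**Step 3: effective arm versus control, Holm over three contrasts, 1.0 SD.** On day 14 alone, ANOVA-based contrasts reach 40–41% and Mann-Whitney 26%. Adjusted, ANCOVA reaches 43 / 52 / 71% and rank ANCOVA 32 / 37 / 47%. At 0.5 SD the figures are 10% against 10 / 12 / 18%, and 6–7% against 8 / 10 / 12%.

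**The case against.** **The gain depends on the comparator.** Section G does not say that the group tests use day 14 alone; change from day 1 fits its wording and the pre/post design equally well. At ρ = 0.7 the normal-outcome gain is 57% to 87% against day-14 values, but only 82% to 87% against change. This stands. Against it, change does no materially better than day 14 at ρ = 0.3 or 0.5, and it does poorly for the 0–3 item. The adjusted analysis is best throughout.

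**The gain can be small.** At ρ = 0.3 and 1.0 SD, ANCOVA adds about 3 points over day-14 ANOVA and rank ANCOVA about 4. This stands too. A reader might infer that the unadjusted group tests are invalid. They are not: they hold their type I error and do compare the four groups.

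**Unnamed outcomes and days.** This is missing detail and partly filled elsewhere, since the legible symptom items carry days and a scale. Other details, such as the definition of the groups, may have stood in text that is not legible. Section G itself reads as a complete paragraph, so that does not supply the missing covariate, contrast or interaction.

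**The third time point.** A reader might infer that Section G contradicts the pre/post design. The documents do not support that. The available text breaks off within the MDA assay description and resumes inside the symptom table, so a third sampling day for the markers may have been stated there. It is a query.

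**Conclusion.** The point holds as one about the choice of analysis. The time tests cannot carry the efficacy conclusion: Friedman has no group factor, and no group-by-time term is stated for repeated-measures ANOVA. The group tests can compare arms but are stated without the baseline value and without a contrast against control. A better method is available from data already collected.

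The conclusion about Friedman follows from the structure of the test and needs no assumed correlation or effect size. The power gain does need them. Across the settings at 1.0 SD it runs from about 3 points (normal outcome, ρ = 0.3, against day 14) to about 30 (ρ = 0.7, against day 14), and only 5 at ρ = 0.7 if change was meant. It would be wrong to quote the largest figure alone, or to present adjustment as a remedy for 10 patients per group. At 0.5 SD every overall test in the day-14 and adjusted comparisons stays below 30%. This should be fixed before outcomes are analysed.

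**What to change.** - For outcomes measured on day 1 and day 14, make the efficacy test the between-group comparison of the day-14 value adjusted for day 1: ANCOVA for continuous biomarkers; rank ANCOVA (such as Quade) or a comparable ordinal method for TNSS items.
- State which of the four groups are control, and name the contrast of each treatment arm with control, with Holm adjustment across them.
- For any outcome with a real third visit, use a model with group, time and group-by-time, and conclude from the group contrast at the final visit.
- Report within-group time tests, including Friedman, as descriptive only.
- Confirm the assessment days for each outcome and reconcile the three-time-point wording with the pre/post design.

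**Cost.** Wording in Section G, with no new patients, visits or assays. Adjustment uses one degree of freedom. Named contrasts have less power than the overall test: at 1.0 SD and ρ = 0.5, about 70% falls to 52% for ANCOVA and about 54% to 37% for rank ANCOVA. Rank ANCOVA gives no effect in score units, so median changes by group should be reported beside it. Quade contrasts under Holm can slightly exceed 5% familywise error: 0.053–0.062 in simulation when one arm has a 1.5 SD effect.

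**Status.** Section G is in the past tense ("Statistical analysis was conducted using IBM SPSS Statistics for Windows, version 25.0"), while Chapter III, B looks ahead ("The research will be carried out after obtaining research approval"). The plan should say which applies. If outcomes have already been analysed, the adjusted analysis must be labelled post hoc.
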